10.10.3.1. Cardiac Monitoring Schedule After First Dose

After the first dose of study treatment on Day 1 of Part 1 and Part 2, participants will be observed up to 8 hours. Cardiac monitoring on the first 4 hours (0H, 1H, 2H, 3H and 4H) is required for all participants. The second 4 hours (5H, 6H, 7H, and 8H) are not required and will only be performed for participants who do not meet discharge criteria at hour 4 of cardiac monitoring. The in-clinic cardiac monitoring on Day 1 will include assessments at the timepoints specified in Table 8. These criteria will also be used at the Part 1 Week 16 visit, the first day of treatment re-initiation following the defined periods of treatment interruption, and for Day 1 Part 2 of the study.

Participants who do not meet discharge criteria at 4 hours postdose on Day 1 will require extended cardiac monitoring on Day 1 (Table 8) and on Day 2, as described in Section 10.10.3.1.2.

For participants who experience a cardiovascular symptomatic event (eg, chest pain, dizziness, palpitations, lightheadedness, shortness of breath, and/or syncope) at any time during the first 4-hours postdose (ie, on Day 1), the Investigator should determine whether or not this event is associated with a HR reduction or clinically relevant change in 12-lead ECG. Participants who experience a symptomatic event associated with HR reduction or clinically relevant 12-lead ECG should be discontinued from study treatment if they meet the criteria described in Section 10.10.3.2. Participants who experience a symptomatic event that is not associated with HR reduction or clinically relevant 12-lead ECG may be discharged on Day 1 at Hour 4 postdose (at the Investigator's discretion and provided they meet the discharge criteria (Section 10.10.3.1.1), but must return to the clinic on Day 2 for extended cardiac monitoring as described in Section 10.10.3.2.

Table 8. Procedures to be Performed During the First-Dose Cardiac Monitoring Period

Procedure	Predose	Hours 1, 2, and 3 Postdose ^a	Hour 4 Postdose ^a	Day 1 Extended Cardiac Monitoring ^b
Blood pressure and HR derived from vital signs (seated position)	Xe	X°	X°	X ^c
12-lead ECG (supine position) ^d	X	_	X	X
Assess discharge criteria	_	_	X	X

- Measurements may be taken within \pm 15 minutes of the scheduled time. Record time of assessment.

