- b Only for participants not meeting discharge criteria (Section 10.10.3.1.1) at Hour 4. Assessments should be repeated hourly (\pm 15 minutes of the scheduled time) until the participant meets the discharge criteria; the blinded study medical monitor should be contacted if the participant does not meet the discharge criteria after 4 hours of extended cardiac monitoring on Day 1. Record time of assessment.
- c If the participant has a vital sign HR of < 50 bpm or if cardiovascular symptoms develop (eg, chest pain, dizziness, palpitations, and/or syncope associated with reduction of HR), conduct 12-lead ECGs as clinically indicated. Include body temperature and respiratory rate.
- d Additional 12-lead ECGs may be conducted as clinically indicated.
- e Include body temperature and respiratory rate.

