10.10.3.1.1. Discharge Criteria After First-Dose Cardiac Monitoring

These criteria will also be used on Day 1 Part 1, at the Week 16 visit of Part 1, first day of treatment re-initiation following the defined periods of treatment interruption, and for Day 1 Part 2 of the study.

Participants will be released from the clinical site after dosing (but no sooner than 4 hours postdose) when they fulfill the following **discharge criteria**:

- 1. Vital sign HR \geq 50 bpm
- If vital sign HR < 50 bpm, then the decrease from baseline must be < 10 bpm
- If participant is meeting the protocol pre-specified discharge criteria at Hour 4, the participant can only be discharged if the lowest HR recorded is not at Hour 4. If Hour 4 HR has the lowest value, the participant needs to be further monitored following extended cardiac monitoring on Day 1 procedures until it is confirmed the HR is on the upward trend before participant is discharged from the site. The full 4 hours of extended cardiac monitoring is not required to establish the upward trend, and participant is not required to return for additional cardiac monitoring on Day 2.
- 2. No evidence from ECG of second-degree AV block or higher
- 3. No participant-reported cardiac symptoms (eg, chest pain, dizziness, palpitations, lightheadedness, shortness of breath, or syncope)

For participants not meeting discharge criteria on Day 1:

- The blinded study medical monitor should be contacted if the participant does not meet the discharge criteria after 4 hours of extended cardiac monitoring on Day 1 (after 8 hour post dose).
- PI and the blinded study medical monitor should come to agreement on how to proceed and if it is appropriate to discharge the participant.
- Participants should have written instructions on when to return to the clinic on Day 2 and a 24-hour contact phone number to call in the event of any new or worsened cardiovascular symptoms.

Additional cardiac-monitoring data collected post Hour 4 needs to be captured on the CRFs.

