Medically qualified personnel as per local clinical practice standards, experienced in interpreting ECGs may perform local ECG reads. If the machine-read is normal, not clinically significant, and the participant meets all other protocol pre-specified discharge criteria, the medically qualified site personnel can choose to discharge the participant based on the local ECG read. If, however, there is any clinical uncertainty, the site should wait for the interpretation by the Central reader prior to discharging the participant.

10.10.3.1.2. Cardiac Monitoring on Day 2 for Participants Not Meeting Discharge Criteria on Day 1 (and Week 16 + 1 day in Part 1)

Table 9 describes extended cardiac monitoring on Day 2 for participants not meeting discharge criteria at 4 hours on Day 1 (Section 10.10.3.1.1) or for participants who experienced a cardiovascular symptomatic event associated with HR reduction or clinically relevant 12-lead ECG during the 4-hour monitoring period on Day 1.

Tabla 0	Procedures to	ho Da	orformed	for Exton	dod Co	rdiac N	Janitaring	on Day 2
i ame 9.	- Procedures 10) ne re	eriorinea	ior rixien	пеп С я	ranacı	Monnoring.	OH DAV Z

Procedure	Predose	Hours 1, 2, 3 Postdose ^a	Hour 4 Postdose ^a
Blood pressure and HR	X^{b}	X ^c	X^c
derived from vital signs			
(seated position)			
12-lead ECG (supine position) ^d	X	_	X
Assess discharge criteria	_	_	X

- Measurements may be taken within \pm 15 minutes of the scheduled time. Record time of assessment.
- b Include body temperature and respiratory rate.
- c If the participant has a vital sign HR of < 50 bpm or if cardiovascular symptoms develop (eg, chest pain, dizziness, palpitations, and/or syncope associated with reduction of HR), the participant should continue to be closely monitored, including 12-lead ECGs as clinically indicated, until the Hour 4 discharge assessment. Include body temperature and respiratory rate.
- d Additional ECGs may be performed as clinically indicated.

10.10.3.2. Study Treatment Discontinuation Related to Postdose Cardiac Monitoring Study treatment discontinuation specific to postdose cardiac monitoring will occur in the following scenarios:

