Appendix 2. Data Derivation Details

Appendix 2.1. Definition and Use of Analysis Visit Windows in Reporting

There are two sets of analysis visit windows, one set for Part 1 (both DB and OLE phases) and another set for Part 2 (OL). For reporting purposes, the analysis visit windows will be used for efficacy and safety display that show by scheduled visits. Observations from all visits including scheduled, unscheduled and early termination visits will all be eligible for allocation to an analysis visit. If two or more observations fall into the same visit window, the observation closest to the target day will be used in the analysis. If there is a tie, the later observation will be used. However, for a participant who discontinues from the study early prior to Week 68 visit window in Part 1 (similarly to Week 52 visit window in Part 2), if two or more observations fall in the same visit window prior to Week 68 in Part 1 (similarly to Week 52 in Part 2), then the latest observation (rather than the observation closest to the target day) within this visit window will be used in the analysis for that visit window.

The analysis visit windowing will be applied after intercurrent events (initation of prohibited medications or discontinuation of study treatment, whichever is earlier) have been accounted for, that is, to the pre-intercurrent-event data and to all data separately (Appendix 3).

Table 8. Analysis Visit Windows for Part 1

Visit Label	Target Day ^a	Window Definition
Baseline	Day 1	Last non-missing assessment on or before Day 1 and prior to first dose of investigational product (ie, etrasimod or placebo)
Week 4	Day 29	Day 2 to Day 42
Week 8	Day 57	Day 43 to Day 70
Week 12	Day 85	Day 71 to Day 98
Week 16 ^b	Day 113	Day 99 to [Treatment Switch Day ^c or Day 126, whichever is smaller]
Week 20	Day 141	[Treatment Switch Day ^c +1 or Day 127, whichever is smaller] to Day 154
Week 24	Day 169	Day 155 to Day 196
Week 32	Day 225	Day 197 to Day 252
Week 40	Day 281	Day 253 to Day 322
Week 52	Day 365	Day 323 to Day 420
Week 68	Day 477	≥ Day 421

a. Target day is equal to the target week \times 7 days + 1 day.

b. All data collected on Week 16 visit, first open-label dose day (treatment switch day), will be included in ≤ Week 16 except for AE data, which will be included in ≥ Week 20. Any new treatment-emergent AE occurred on the day of first open-label dose (treatment switch day) will be included in ≥ Week 20.

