c. Day of first open-label dose at Week 16 = Treatment switch day (ie, treatment switch day = treatment switch date – date of the first dose +1), where treatment switch date is taken from the Treatment Dosing CRF, as the start date in the first entry of the Treatment Dosing log for the period of Week 16 to Week 20.

Note that the upper limit of the Week 16 visit window and the lower limit of the Week 20 visit window are defined uniquely for each of the participants in the study regardless of which treatment group the participants are randomized to.

If treatment switch day (ie, day of first open-label etrasimod dose) falls between Day 99 and Day 126, then the upper limit of the Week 16 visit window is the smaller of treatment switch day or Day 126, and the lower limit of the Week 20 visit window is the smaller of treatment switch day+1 or Day 127.

In the unlikely case if treatment switch day < Day 99, > Day126, or missing (eg, discontinuation of study treatment or study prior to Week 16), then the upper limit of the Week 16 visit window will be set to Day 126 and the lower limit of the Week 20 visit window will be set to Day 127.

Table 9. Analysis Visit Windows for Part 2

Visit Label	Target Day ^a	Window Definition
Baseline	Day 1	Last non-missing assessment on or before Day 1 and prior to first dose of etrasimod
Week 4	Day 29	Day 2 to Day 42
Week 8	Day 57	Day 43 to Day 84
Week 16	Day 113	Day 85 to Day 140
Week 24	Day 169	Day 141 to Day 210
Week 36	Day 253	Day 211 to Day 280
Week 44	Day 309	Day 281 to Day 336
Week 52	Day 365	≥ Day 337

a. Target day is equal to the target week \times 7 days + 1 day.

For safety data collected for participants who complete the 2-week and 4-week follow-up visits (Weeks 70 and 72 in Part 1 OLE, Weeks 54 and 56 in Part 2 OL Safety phase), available safety data will be summarized for these nominal visits.

For 12-Lead ECG collected on Day 1 during first-dose cardiac monitoring, the labels for timepoints can be "Day 1 Predose", "Day 1 1HR Postdose" to "Day 1 4HR Postdose".

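### The SAP's visit windows misplace first-dose cardiac monitoring data: Day 2 is shown as Week 4, and a reading taken after the first open-label dose can become the double-blind Week 16 value

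*SAP*

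**What the plan says.** **What is collected.** Under Protocol 10.10.3.1, after the first dose "participants will be observed up to 8 hours". Hours 1 to 4 apply to everyone; hours 5 to 8 apply only to those who do not meet the discharge criteria at hour 4. For that extended period the notes to Table 8 say "Assessments should be repeated hourly", and the table includes both vital signs and ECG. Protocol 10.10.3.1.1 adds: "Additional cardiac-monitoring data collected post Hour 4 needs to be captured on the CRFs". Protocol 10.10.3.1.2 continues: "Table 9 describes extended cardiac monitoring on Day 2 for participants not meeting discharge criteria at 4 hours on Day 1". Table 9 schedules vital signs pre-dose and at hours 1 to 4, and ECGs pre-dose and at hour 4. Protocol 10.10.3 applies the same procedures to the first open-label dose at Week 16 of Part 1 and to re-initiation after a defined interruption.

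**How it is to be displayed.** SAP Appendix 2.1 says of the windows that "the analysis visit windows will be used for efficacy and safety display that show by scheduled visits", and that "Observations from all visits including scheduled, unscheduled and early termination visits will all be eligible for allocation to an analysis visit". The baseline window in Table 8 is "Last non-missing assessment on or before Day 1 and prior to first dose of investigational product". In both parts the next window, Week 4, runs from Day 2 to Day 42 with target Day 29. Within a window the observation nearest the target day is used, and the later one if there is a tie. For someone who leaves the study early, the latest observation in the window is used. Footnote b to SAP Table 8 keeps everything collected on the treatment-switch day in Week 16 or earlier, except adverse events. The only text on monitoring time points is the sentence beginning "For 12-Lead ECG collected on Day 1 during first-dose cardiac monitoring, the labels for timepoints can be", which lists pre-dose and 1 to 4 hours.

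SAP 6.5.4 summarizes ECG heart rate and PR interval only as change from baseline by treatment and time. Its extreme-value tables cover QT and QTcF.

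**The concern.** Bradycardia and AV conduction delay are adverse events of special interest. Clinically significant ECG and vital-sign changes are primary endpoints for the Part 1 OLE and Part 2. Extended and Day 2 monitoring is done in participants who did not clear the hour-4 criteria or had a cardiovascular event on Day 1, and extended Day 1 monitoring also covers those whose heart rate was lowest at hour 4. These records are the most informative about the first-dose effect. The by-time ECG table, which is the one display specified for ECG heart rate and PR, has no place for them or puts them under the wrong week.

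The Week 16 case is different in kind, because it touches the comparison of arms. Protocol 2.3.1 describes a heart-rate reduction on first dosing with this drug class. If a placebo participant's Week 16 value is taken hours after the first etrasimod dose, the double-blind placebo summary contains an etrasimod first-dose effect. The interim data cut (SAP Section 7) includes all safety data up to the Week 16 visit, and ECG and vital-sign changes are among the data reviewed for the go/no-go decision.

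**Working it through.** The plan states no figure on this point, so there is none to reproduce. The check is to apply the windows and selection rules of SAP Appendix 2.1 to the records that the protocol collects.

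1. **Day 1, hours 5 to 8 (both parts).** Baseline is pre-dose only and Week 4 starts on Day 2, so no visit window contains a Day 1 post-dose value. Placement depends on the ECG labels alone, and these end at 4 hours. Result: no window and no label.

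2. **Day 2 ECG, participant continues (both parts).** Day 2 lies in Days 2 to 42. The Schedule of Activities has ECGs at Screening, Day 1, Week 16 and Week 68 in Part 1, and at Screening, Day 1, Week 16 and Week 52 in Part 2, besides early-termination and follow-up visits. None is scheduled at Week 4, so the Day 2 ECG has no scheduled competitor. The pre-dose and hour-4 readings tie on day, and the later is used. Result: the Day 2 hour-4 ECG is shown as Week 4.

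3. **Day 2 vital signs, participant continues.** The distance to target is |2 − 29| = 27 days. The Week 4 visit (Day 29 ± 5) is at most 5 days from target. Result: the Week 4 visit is selected and Day 2 drops out of the by-visit display.

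4. **Participant stopped after Day 2.** Protocol 10.10.3.2 requires an early-termination visit with ECG within 3 calendar days. Take Day 5 as an example. If the participant leaves the study, the latest-observation rule selects Day 5. If the nearest-to-target rule applies instead, |5 − 29| = 24 is less than 27, and Day 5 is again selected over Day 2. Result: the early-termination ECG is shown as Week 4 and Day 2 is not displayed there.

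5. **Day after the first open-label dose.** With the switch on Day 113, the Week 16 window ends on Day 113 and Week 20 starts on Day 114. No ECG is scheduled at Week 20, so the Day 114 ECG is shown as Week 20. For vital signs, |114 − 141| = 27 exceeds the at most 5 days of the actual Week 20 visit, so Day 114 is not selected.

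6. **Switch day itself.** ECGs are taken before dosing and 4 hours after; vital signs are taken before dosing and at hours 1 to 4. All carry the same study day, so all are equally far from Day 113 whatever the switch day is. Footnote b keeps them in Week 16, and the tie goes to the later observation. Result: the post-dose reading can be selected as the Week 16 value in either arm. The tie arises for anyone who takes the open-label dose with readings on both sides of it, not only for those in extended monitoring.

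**The case against.** The strongest reply is that little is at risk. The windows govern only displays by scheduled visit. The label sentence is permissive and excludes nothing. Several other summaries do not depend on either: maximum post-dose QTcF and QT above 500 ms (SAP 6.5.4), vital signs by time post-dose with participant counts of clinically significant change (6.5.3), the clinically significant change endpoint (3.5.1), and adverse-event and AESI summaries (3.5.2, 6.5.1). AV block would be seen through adverse-event reporting, not through a mean by time. Safety displays also follow the sponsor's standards, which are not in these documents and may add more. All safety analysis is descriptive, and the E-DMC monitors safety separately.

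Most of this stands, and it limits the point. A reader might infer that data after hour 4 are lost; they are not, because the CRF holds them and the tables just named can use them. A reader might infer that the first-dose effect is understated on Day 1. That would need a heart-rate low after hour 4, which no document shows, and everyone's hour 1 to 4 vital signs and hour-4 ECG keep their time points. Labels for ECGs at hours 1 to 3 are not an error either, since the notes to Table 8 allow ECGs then if clinically indicated.

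The reply does not answer the misplacement. Nothing in the SAP exempts monitoring records from windowing, all observations are expressly eligible, and footnote b with the tie rule is an explicit instruction. For ECG heart rate and PR, SAP 6.5.4 specifies no extreme-value table to stand in for the by-time display.

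**Conclusion.** The point holds for by-visit and by-timepoint safety displays, chiefly ECG heart rate and PR interval. As written, Day 2 ECGs are allocated to Week 4 and ECGs from the day after the open-label dose to Week 20. Vital signs from those days lose to the actual visits. Day 1 hours 5 to 8 have no ECG label. A reading taken after the first open-label etrasimod dose can become the double-blind Week 16 value, including for placebo participants.

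The number affected cannot be computed. The documents give no rate of failing the hour-4 criteria or of Day 2 monitoring, and they do not state how many of the approximately 60 Part 1 participants will enter the OLE. Treating the hourly readings as exchangeable would produce a count, but that assumes no time course of drug effect, contrary to Protocol 2.3.1.

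The conclusion assumes that Appendix 2.1 is programmed literally and that the sponsor's display standards do not override it. It concerns descriptive safety tables only. Efficacy at Week 16 is not affected by the switch-day tie, because those assessments are to be completed before dosing.

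**What to change.** In SAP Appendix 2.1, define first-dose monitoring as its own analysis period: Day 1 pre-dose, post-dose hours through 8, and Day 2. Define matching periods for the Week 16 switch day post-dose and the day after, and for re-initiation. Exclude the post-dose and next-day monitoring records from visit windowing. State that only the pre-dose ECG and vital signs on the switch day supply the double-blind Week 16 value.

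In SAP 6.5.3 and 6.5.4, add per-participant lowest heart rate, largest fall in heart rate and longest PR interval over the monitoring period, by arm and dosing occasion. These serve better than means at hours 5 to 8, which would describe only the participants still being observed.

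The cost is SAP wording and a few table rows. No new data are needed and no clinical procedure changes.

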Appendix 2.2. Endpoint Derivations

Appendix 2.2.1. Investigator's Global Assessment (IGA)

IGA of AD is scored on a 5-point scale (0-4), reflecting a global consideration of the erythema, induration, and scaling. The clinical evaluator of AD will perform an assessment of the overall severity of AD and assign an IGA score: 0=clear, 1=almost clear, 2=mild, 3=moderate, or 4=severe. The assessment will be a static evaluation without regard to the

score at a previous visit. According to protocol's inclusion criteria, only participants with IGA score ≥3 at screening and baseline (Day 1) are included in this study. The following binary efficacy endpoints will be derived based on IGA score at a visit.

- IGA response: IGA score of clear (0) or almost clear (1) on a 5-point scale and a reduction from of ≥2 from baseline. Only participants with baseline IGA ≥2 are included in all analyses of this endpoint.
- IGA score of clear (0) or almost clear (1) on a 5-point scale.

Appendix 2.2.2. Body Surface Area (BSA)

BSA affected by AD will be determined by the participant's handprint method, where the full hand of the participant (ie, the participant's fully extended palm, fingers, and thumb together in a closed position) represents approximate 1% of the total BSA. The BSA AD involvement ranges from 0% to 100%, with higher values representing greater severity of AD. The BSA is performed separately for 4 regions of the body: Region 1 − head and neck; Region 2 − trunk (including genital area); Region 3 − upper limbs; and Region 4 − lower limbs (including buttocks). The total number of handprints in each body region is given in the following table. The total number of handprints summed up across the 4 body regions is 100, which is used as the denominator for total BSA. Total BSA efficacy (%) will be derived from the sum of the BSA in handprints across 4 body regions (out of total of 100), and it is assessed as part of the EASI assessment (Appendix 2.2.3). According to protocol's inclusion criteria, only participants with BSA ≥10% of AD involvement at screening and baseline (Day 1) are included in this study.

Table 10. Handprint Determination of BSA

Body Region	Total Number of Handprints in Body Region*	Surface Area of Body Region Equivalent of One Handprint*
Head and Neck (h)	10	10%
Upper Limbs (u)	20	5%
Trunk (including axillae and groin/genitals) (t)	30	3.33%
Lower Limbs (including buttocks) (l)	40	2.5%

^{*}Handprint refers to the hand size of each individual participant.

Further, the extent (%) of each of the four body region (h, u, t, and l) will be determined by dividing the number of BSA handprints by the total (maximum) number of handprints for that body region (range: 0% to 100%). For example, if there are 3 BSA handprints for Head and Neck region, the extent (%) of the Head and Neck region is (3/10) x 100% = 30%. This extent (%) to which each of the four body regions (h, u, t, and l) is involved with atopic dermatitis is categorized (ie, mapped) to a numerical Area Score (Ah, Au, At, and Al, respectively) using a non-linear scaling method according to the following BSA scoring criteria. Using the same previous example, Ah is 3.

Percent BSA with AD in a body region (h, u, t, and l) Area Score (Ah, Au, At, and Al) >0 - <10% 10 - < 30% 2 30 - < 50% 3 50 - < 70% 4 70 - < 90% 5 90 - 100%

6

Table 11. Mapping of Body Region BSA Percentage to Area Score

These Area Scores (Ah, Au, At, and Al) of the four body regions will be used to derive the EASI score (Appendix 2.2.3). If any one of the four body regions has missing number of BSA handprints, the extent (%) of BSA in this body region will be missing and so will the Area Score for this body region. The total BSA (%) will also be missing.

